**Table 7.1.6.2 EPQs: Change from Baseline at Week-12**

Domain	Baseline	Week 12	CFB in Proportion at Week-12	p-value
	(N=x)	(N=x)	(N=x)	
Emotional Functioning				
EPQ1 (AH1): Over the past 7 days, how often has your acne made you feel angry (mad/sad)?	n (%)	n (%)	%	P
Never / Rarely	n (%)	n (%)	%	P
Most of the time / All of the time	n (%)	n (%)	%	
Some of the time				
EPQ2 (AH2): How worried are you about how long your acne will last and how bad it will get?				
Not at all / Slightly	n (%)	n (%)	%	P
Moderately / Extremely	n (%)	n (%)	%	P
Somewhat	n (%)	n (%)	%	
EPQ3 (AH3): How often do you think about your acne?				
Never / Rarely	n (%)	n (%)	%	P
Most of the time / All of the time	n (%)	n (%)	%	P
Some of the time	n (%)	n (%)	%	
EPQ4 (AH4): Over the past 7 days, how worried have you been about your acne?				
Not at all / Slightly	n (%)	n (%)	%	P
Moderately / Extremely	n (%)	n (%)	%	P
Somewhat	n (%)	n (%)	%	
Social Functioning				
EPQ5 (AH5): How often do you change, edit, or filter your social media photo or selfie because of your acne?				
Never / Rarely	n (%)	n (%)	%	P

	n (%)	n (%)	%	P
Most of the time / All of the time				
Some of the time	n (%)	n (%)	%	
EPQ6 (AH6): How often does acne impact your “in real-life” plans (IRL) (like dating or social engagements, playing sports, swimming, or hanging out)?				
Never / rarely	n (%)	n (%)	%	P
Most of the time / all of the time	n (%)	n (%)	%	P
Some of the time	n (%)	n (%)	%	
EPQ7 (AH7): How often are you doing something to hide your acne (like mess with, squeeze/pop, or use makeup, concealer, hairstyle, clothes to cover up)?				
Never / rarely	n (%)	n (%)	%	P
Most of the time / all of the time	n (%)	n (%)	%	P
Some of the time	n (%)	n (%)	%	
Activities of Daily Living				
EPQ8 (AH8): How often do you feel picked on or judged because of your acne?				
Never / rarely	n (%)	n (%)	%	P
Most of the time / all of the time	n (%)	n (%)	%	P
Some of the time	n (%)	n (%)	%	
EPQ9 (AH9): How concerned are you that your acne will affect your ability to reach your future goals (in school or work) and be the best you can be?				
Not at all / Slightly	n (%)	n (%)	%	P
Moderately / Extremely	n (%)	n (%)	%	P
Somewhat	n (%)	n (%)	%	

**EPQ10 (AH10):** Do you feel that your parents understand your acne-related concerns?

Not at all / A little	n (%)	n (%)	%	P
Quite a bit / Very much	n (%)	n (%)	%	P
Somewhat	n (%)	n (%)	%	

**EPQ11 (AH11):** Over the past 7 days, how often has worrying about or discomfort (itching/hurting) from acne affected your sleep?

Never / rarely	n (%)	n (%)	%	P
Most of the time / all of the time	n (%)	n (%)	%	P
Some of the time	n (%)	n (%)	%	

Note: X patients had missing data; The denominator for the percentage is the number of patients with available data (N=X)

**Table 7.1.7.1. Sub-group analysis of EPQ 1**

**AH1:** Over the past 7 days, how often has your acne made you feel angry (mad/sad)? Subjects who selected *Never/Rarely*.

	Baseline (N=x)	Week 12 (N=x)
Sex		
Male	n (%)	n (%)
Female	n (%)	n (%)
p -value	p	p
Age Group		
≥ 9 and < 12 years	n (%)	n (%)
≥ 12 and < 18 years	n (%)	n (%)
≥ 12 years	n (%)	n (%)
p -value	p	p
Race		
White	n (%)	n (%)
African America/Black	n (%)	n (%)
Other	n (%)	n (%)
p -value	p	p
Body mass index		
< 25 kg/m 	n (%)	n (%)
≥ 25 kg/m 	n (%)	n (%)
p -value	p	p
Baseline facial IGA		
Moderate	n (%)	n (%)
Severe	n (%)	n (%)
p -value	p	p
Female who used oral contraceptive*		
Used	n (%)	n (%)
Did not use	n (%)	n (%)
p -value	p	p

Note: The denominator for the percentage is the number of subjects with available data who selected *Never/Rarely* (N=X for Baseline and N=X for Week-12).

\*The denominator for the percentage is the number of 'female' subjects with available data who selected *Never/Rarely* (N=X for Baseline and N=X for Week-12).

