### Understanding of Acne-related Concerns

Pediatric patients (of age 12-17) were asked whether their parents understand their acne-related concerns, and correspondingly, the parents/caregivers were asked whether they understand their

child's acne-related concerns. This pair of questions have a response item on a 5-point likert scale of 'not at all' to 'very much'. These questions were asked at baseline and Week 12.

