## 6.3 General Statistical Procedures

### 6.3.1 Overview

Data from Site Investigators and study Subjects will be treated separately, and combined into one dataset, based on the study assessments of interest. Validated instruments will be scored according to developer guidelines, reporting domain scores and overall summary scores, as appropriate. Home-grown questions/items will be analyzed and reported individually, based on the respective response scales. Change from Baseline (CFB) in scores (for continuous variables) or proportions (for discrete variables) will be computed as Week-12 minus Baseline measure for respective question responses.

Discrete measures will be assessed using summary statistics encompassing percentage of Subjects reporting particular outcome measures. The statistical differences in discrete variables to compare different patient groups (for subgroup analysis) for a given measure at a particular timepoint (such as Baseline or Week-12), or CFB in proportion of patients reporting a particular response to an outcome measure at a particular timepoint (such as Week-12) will be assessed using a  $\chi^2$  test. In case of likert scales, to compute P-values for CFB in proportions, the top-two response categories (of a likert scale) for a given question at Baseline will be grouped together into a single group proportion (versus the rest of the population/responders all together) and compared to the same group proportion at Week-12; the procedure will be repeated for the bottom-two response categories (of a likert scale) for a given question, by grouping them together into a single group proportion and compare it to the same group proportion at Week-12. For example, for ASIS item # 1 (how oily is your face right now), proportion of patients reporting “Not at all/A little” at Baseline will be grouped together (vs. rest of the population/responders) and compared to proportion of patients reporting “Not at all/A little” at Week-12; similarly, proportion of patients reporting “Quite a bit/Very” at Baseline will be grouped together and compared to proportion of

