patients reporting “Quite a bit/Very” at Week-12, to compute respective P values. Continuous measures will be assessed using summary statistics; paired sample t-tests will be used to assess statistical differences for CFB evaluations, while independent sample t-tests will be used to assess statistical differences between different patient groups (for subgroup analysis) for a given measure at a particular timepoint (such as Baseline or Week-12).

Computation of statistical differences will be performed only as an exploratory step (and not for hypothesis testing), considering the descriptive nature of the study; for such exploratory evaluation, P value  $\leq 0.05$  will be considered significant. All statistical analyses will be based on all available data assuming that all missing data are uninformative and will be conducted using appropriate statistical software, such as SAS.

An interim analysis will be conducted using FAS, upon completion of 12 weeks of data collection (from both patients and clinicians) for ~200 study Subjects, using the statistical methods identical to the analyses planned for FAS-based final data analyses; the focus of the interim analyses will be the primary objective, secondary objective and select additional objectives, as outlined below; no subgroup analyses will be considered.

- FAS cohort demographics
- PROs: Antibiotic attitudes at baseline
- PROs: CFB in EPQ measures
- PROs: CFB in ASIS measures
- PROs: CFB in Patient Acne Severity and How Face Looks (with and without LOCF imputation)
- PROs: CFB in Parent/caregiver concerns about the child with Acne:
  - Understanding child's concerns
  - Concerned about child's acne
  - Concerned about child's ability to accomplish future goals
- Facial IGA and Facial IGA success (with and without LOCF imputation)
- Select comparison of patient and clinician reported measures: Acne Severity (with LOCF imputation)

- Select comparison of pediatric patient and caregiver reported measures:
  - Understanding child's concerns
  - Concerned about child's acne
  - Concerned about child's ability to accomplish future goals
- Clinician satisfaction with sarecycline
- Sarecycline treatment characteristics

The description of the individual study measures are outlined in the forthcoming sections.

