### **6.3.2 *Subgroup Analysis***

Primary and select additional outcome measures (as individually identified in the following sections) will be summarized and repeated for the following subgroups, using FAS:

- Gender: male and female
- Age groups: 9 to 17 years and  $\geq 18$  years
- Race: white, african-american/black, other

- Body mass index: < 25 kg/m^2 and ≥ 25 kg/m^2
- Baseline facial IGA score: moderate and severe
- Concomitant use of contraceptives in females: yes and no

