#### 6.4 Primary Endpoint Analysis

The primary endpoint of PROs at Week 12 will be assessed descriptively, using the FAS dataset.

For ASIS questionnaire, the individual item and domain/subscale scores will be created per instrument developer instructions, analyzed descriptively for the baseline and Week 12 encounters, treating the responses as categorical variables and/or continuous variable, as appropriate. For the overall questionnaire data evaluation, no missing data imputation will be applied to compute domain/subscale scores.

The Patient Global Assessment (PtGA) of acne severity based on the single ASIS item (# 9) will be analyzed separately using descriptive statistics and reported for Week 12. Specifically, proportion of Subjects who reported clear (0) and almost clear (1) on the item scale at Week 12 will be assessed. Last Observation Carried Forward (LOCF) data imputation method will be used to impute responses to ASIS item # 9 at Week 12 for the Subjects with missing data at Week 12.

Patient self-rating of their appearance based on the single ASIS Item (# 10) will be analyzed separately using descriptive statistics and reported for Week 12. Specifically, proportion of Subjects reporting "very good" or "excellent" at Week 12 will be assessed. LOCF data imputation method will be used to impute responses to ASIS item # 10 at Week 12 for the Subjects with missing data at Week 12.

For EPQ, the items will be analyzed individually using descriptive statistics and reported for Week 12.

For all PRO elements, descriptive statistics will be computed. ASIS summary domain scores, ASIS item # 9, ASIS item # 10, and individual EPQ items will be stratified by age and other subgroups outlined in Section 6.3.2, to explore the relationship between these HRQoL items and subject characteristics.

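### The 11 EPQ subgroup tables print each subgroup's share of responders instead of its response rate, and 15 of the 17 subgroup tables with age rows print overlapping age bands

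*SAP*

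**What the plan says.** **Denominator.** Each of the 11 EPQ subgroup tables (SAP Tables 7.1.7.1 to 7.1.7.11) shows n (%) at Baseline and Week 12 for one pair of response categories, with a p-value for each subgroup factor. The table note reads "The denominator for the percentage is the number of subjects with available data who selected" that response. For the contraceptive rows the base is the "number of 'female' subjects with available data who selected" it. The overall EPQ table (7.1.6.2) instead uses all patients with available data.

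**Test and purpose.** SAP 6.3.1 assigns a chi-square test to "The statistical differences in discrete variables to compare different patient groups (for subgroup analysis) for a given measure at a particular timepoint". SAP 6.4 says the stratification is meant "to explore the relationship between these HRQoL items and subject characteristics".

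**Age rows.** SAP 6.3.2 and Protocol 12.3.2 list two groups: "Age groups: 9 to 17 years and" 18 years or over. All 17 subgroup tables with age rows print three. In 15 of them the rows are 9 to under 12, 12 to under 18, and 12 and over: the 11 EPQ tables and Tables 7.1.16.2, 7.2.4.5, 7.2.4.8 and 7.2.9. Only Tables 7.1.11 and 7.1.16.1 print 18 and over as the third row.

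**Two smaller points.** SAP 5.4 states: "Pediatric patients (of age 12-17) were asked whether their parents understand their acne-related concerns". Table 7.1.7.10 nevertheless compares age groups on that question. Table 7.1.11 gives one p-value each for race and age, both with three levels, while SAP 6.3.1 names only an independent-sample t-test for subgroup differences in continuous measures.

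**The concern.** A subgroup table should let the reader compare how often each subgroup gave the response. With responders as the base, a large subgroup gets a large percentage whatever its response rate. The number of subjects per subgroup row is not printed, so the rate cannot be worked out from the table. The chi-square, if run on full subgroup-by-response counts, does compare rates, so its p-value stands beside percentages it does not compare. Someone reading the EPQ results by sex, race or BMI could take the wrong direction from them.

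The age rows as printed count ages 12 to 17 twice and have no adult row. A chi-square test across overlapping rows is not valid. One of the affected tables, 7.2.4.8, is the subgroup display for the secondary endpoint.

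**Working it through.** **Counts, from reading every subgroup shell.** The responder-only denominator is in 11 of 11 EPQ subgroup tables. Seventeen subgroup tables have age rows: the 11 EPQ tables plus 7.1.11, 7.1.16.1, 7.1.16.2, 7.2.4.5, 7.2.4.8 and 7.2.9. Table 7.5.1 splits only by visit type and is not counted. The row for 12 and over is in 11 + 4 = 15 of the 17.

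**Formula.** With n_g subjects in subgroup g and response rate r_g, the printed percentage is n_g r_g / Σ(n_k r_k). The percentage needed is r_g.

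**Inputs.** The plan has no figure to reproduce, and the documents give no subgroup sizes or response rates. Assumed here: 250 subjects with data, and a male share of 20% to 50%.

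**Equal rates.** The rate cancels and the printed value is n_g / N. Take 100 males and 150 females, with both rates rising from 20% to 60%:
- Baseline: 20/50 = 40% male, 30/50 = 60% female.
- Week 12: 60/150 = 40% male, 90/150 = 60% female.

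The counts and column Ns triple, but the percentages do not move. For male shares of 20%, 30%, 40% and 50% the table prints 20/80, 30/70, 40/60 and 50/50 at both visits.

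**Unequal rates: 60% in males, 40% in females.** Chi-square is Pearson without continuity correction.

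| Males / females | Responders M / F | Printed M / F | Chi-square | p |
|---|---|---|---|---|
| 50 / 200 | 30 / 80 | 27.3% / 72.7% | 6.49 | 0.011 |
| 75 / 175 | 45 / 70 | 39.1% / 60.9% | 8.45 | 0.0036 |
| 100 / 150 | 60 / 60 | 50.0% / 50.0% | 9.62 | 0.0019 |
| 125 / 125 | 75 / 50 | 60.0% / 40.0% | 10.0 | 0.0016 |

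The printed order agrees with the true order only when the male share exceeds r_F / (r_M + r_F) = 0.4 / (0.6 + 0.4) = 40%. In the last row the printed values equal the rates only because the groups are the same size and the two rates happen to sum to 100%.

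**Age rows taken literally.** In the EPQ tables the three age percentages sum to 100% plus the share of responders aged 12 to 17. At equal rates, sizes for 9-11 / 12-17 / 18+ of 10/50/190, 10/100/140 and 10/150/90 give 120%, 140% and 160%. With 18 and over as the third row they sum to 100%.

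**Small cells if three bands are kept.** Assume responders of 6/10, 50/100 and 91/140, which is 147/250 = 58.8% overall. The smallest expected count is 10 × 0.412 = 4.12. With two groups (56/110 and 91/140) it is 110 × 0.412 = 45.3.

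**The case against.** The strongest reply is that the display is poor but neither hidden nor harmful. Each table is headed as covering subjects who chose the response, and its note states the base. Table 7.1.11 is laid out for the same factors and visits with an n in the cells. SAP section 7 expects Week 12 responders to have answered all PRO questions, so EPQ counts divided by those n should come close to the rates. The age label is an obvious slip that a programmer would resolve from SAP 6.3.2. Three bands nest within the two, and they separate proxy answers (ages 9 to 11) from self-report. Protocol 12.3.1 already allows any appropriate test for continuous measures. SAP 6.3.1 makes all these tests exploratory, and the sizes above are assumed.

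Much of this is fair as a limit on scope. Rates could be pieced together across tables for most items, though not for the parent-understanding item, which went to ages 12 to 17 only. The proxy split is a sound reason to prefer three bands. The 40% break-even belongs to the rate pair chosen; the example shows that a reversal is possible, not that it is likely. The missing three-group test is a gap in SAP wording only.

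None of it makes the printed percentages answer the question in SAP 6.4. Disclosing the base does not turn a composition into a rate. Resolving the label by reference to SAP 6.3.2 still leaves three rows in the shells against two groups in the text.

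**Conclusion.** The concern holds and should be fixed before the tables are programmed. Followed as written, all 11 EPQ subgroup tables report the make-up of responders. That the percentages are not response rates follows from the notes alone; how far they mislead depends on the assumed sizes and rates. In the examples they hide a threefold rise in both sexes, and they reverse a 60% v 40% difference whenever males are under 40% of the cohort.

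The age rows overlap in 15 of 17 tables, and all 17 depart from the prespecified groups. The overlap is probably a labelling error, but as printed the age p-values in those 15 tables are invalid.

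The scope is limited. These are exploratory subgroup tables, and the overall primary and secondary estimates are unaffected. Chi-square p-values for factors other than age are sound if run on full subgroup-by-response counts. The race p-value in Table 7.1.11 has no applicable test named in the SAP.

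**What to change.** 1. In Tables 7.1.7.1 to 7.1.7.11, set the denominator to the number of subjects in that subgroup row with available data at that visit, with contraceptive users and non-users each having their own, and print that number. At the same time, state whether N in the notes to Tables 7.2.4.5, 7.2.4.8 and 7.2.9 is per subgroup row.
2. Make the age rows disjoint and identical in all 17 tables and in SAP 6.3.2. Either use the two prespecified groups (9-17, 18 and over), or keep three bands (9-11, 12-17, 18 and over) and amend 6.3.2 to match. With three bands, use an exact test where an expected count is below 5.
3. Drop the age comparison from Table 7.1.7.10.
4. For Table 7.1.11, name one-way ANOVA for three-level factors (race, and age if three bands are kept) and keep the t-test for two-level factors.

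The cost is edits to table notes and row labels, a matching line in SAP 6.3.2 if three bands are kept, and one sentence on the test for three-level factors. No new data are needed.

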**Table 7.1.7.2. Sub-group analysis of EPQ 2**

**AH2:** How worried are you about how long your acne will last and how bad it will get? Subjects who selected *Not at all/Slightly*.

	Baseline (N=x)	Week 12 (N=x)
Sex		
Male	n (%)	n (%)
Female	n (%)	n (%)
p -value	p	p
Age Group		
≥ 9 and < 12 years	n (%)	n (%)
≥ 12 and < 18 years	n (%)	n (%)
≥ 12 years	n (%)	n (%)
p -value	p	p
Race		
White	n (%)	n (%)
African America/Black	n (%)	n (%)
Other	n (%)	n (%)
p -value	p	p
Body mass index		
< 25 kg/m 	n (%)	n (%)
≥ 25 kg/m 	n (%)	n (%)
p -value	p	p
Baseline facial IGA		
Moderate	n (%)	n (%)
Severe	n (%)	n (%)
p -value	p	p
Female who used oral contraceptive*		
Used	n (%)	n (%)
Did not use	n (%)	n (%)
p -value	p	p

Note: The denominator for the percentage is the number of subjects with available data who selected *Not at all / Slightly* (N=X for baseline and N=X for week 12)

\*The denominator for the percentage is the number of 'female' subjects with available data who selected *Not at all / Slightly* (N=X for Baseline and N=X for Week-12).

**Table 7.1.7.3. Sub-group analysis of EPQ 3**

**AH3:** How often do you think about your acne? Subjects who selected Never/Rarely.

	Baseline (N=x)	Week 12 (N=x)
Sex		
Male	n (%)	n (%)
Female	n (%)	n (%)
p-value	p	p
Age Group		
≥ 9 and < 12 years	n (%)	n (%)
≥ 12 and < 18 years	n (%)	n (%)
≥ 12 years	n (%)	n (%)
p-value	p	p
Race		
White	n (%)	n (%)
African America/Black	n (%)	n (%)
Other	n (%)	n (%)
p-value	p	p
Body mass index		
< 25 kg/m 	n (%)	n (%)
≥ 25 kg/m 	n (%)	n (%)
p-value	p	p
Baseline facial IGA		
Moderate	n (%)	n (%)
Severe	n (%)	n (%)
p-value	p	p
Female who used oral contraceptive*		
Used	n (%)	n (%)
Did not use	n (%)	n (%)
p-value	p	p

Note: The denominator for the percentage is the number of subjects with available data who selected Never/Rarely (N=X for baseline and N=X for week 12).

\*The denominator for the percentage is the number of 'female' subjects with available data who selected Never/Rarely (N=X for Baseline and N=X for Week-12).

**Table 7.1.7.4. Sub-group analysis of EPQ 4**

**AH4:** Over the past 7 days, how worried have you been about your acne?  
Subjects who selected *Not at all / Slightly*.

	Baseline (N=x)	Week 12 (N=x)
Sex		
Male	n (%)	n (%)
Female	n (%)	n (%)
p-value	p	p
Age Group		
≥ 9 and < 12 years	n (%)	n (%)
≥ 12 and < 18 years	n (%)	n (%)
≥ 12 years	n (%)	n (%)
p-value	p	p
Race		
White	n (%)	n (%)
African America/Black	n (%)	n (%)
Other	n (%)	n (%)
p-value	p	p
Body mass index		
< 25 kg/m 	n (%)	n (%)
≥ 25 kg/m 	n (%)	n (%)
p-value	p	p
Baseline facial IGA		
Moderate	n (%)	n (%)
Severe	n (%)	n (%)
p-value	p	p
Female who used oral contraceptive*		
Used	n (%)	n (%)
Did not use	n (%)	n (%)
p-value	p	p

Note: The denominator for the percentage is the number of subjects with available data who selected *Not at all / Slightly* (N=X for baseline and N=X for week 12).

\*The denominator for the percentage is the number of 'female' subjects with available data who selected *Not at all / Slightly* (N=X for baseline and N=X for week 12).

**Table 7.1.7.5. Sub-group analysis of EPQ 5**

**AH5:** How often do you change, edit, or filter your social media photo or selfie because of your acne? Subjects who selected *Never / Rarely*

	Baseline (N=x)	Week 12 (N=x)
Sex		
Male	n (%)	n (%)
Female	n (%)	n (%)
p-value	p	p
Age Group		
≥ 9 and < 12 years	n (%)	n (%)
≥ 12 and < 18 years	n (%)	n (%)
≥ 12 years	n (%)	n (%)
p-value	p	p
Race		
White	n (%)	n (%)
African America/Black	n (%)	n (%)
Other	n (%)	n (%)
p-value	p	p
Body mass index		
< 25 kg/m 	n (%)	n (%)
≥ 25 kg/m 	n (%)	n (%)
p-value	p	p
Baseline facial IGA		
Moderate	n (%)	n (%)
Severe	n (%)	n (%)
p-value	p	p
Female who used oral contraceptive*		
Used	n (%)	n (%)
Did not use	n (%)	n (%)
p-value	p	p

Note: The denominator for the percentage is the number of subjects with available data who selected Never/Rarely (N=X for baseline and N=X for week 12).

\*The denominator for the percentage is the number of 'female' subjects with available data who selected Never/Rarely (N=X for baseline and N=X for week 12).

**Table 7.1.7.6. Sub-group analysis of EPQ 6**

**AH6:** How often does acne impact your “in real-life” plans (IRL) (like dating or social engagements, playing sports, swimming, or hanging out)?  
Subjects who selected *Never / Rarely*.

	Baseline (N=xx)	Week 12 (N=xx)
Sex		
Male	n (%)	n (%)
Female	n (%)	n (%)
p-value	p	p
Age Group		
≥ 9 and < 12 years	n (%)	n (%)
≥ 12 and < 18 years	n (%)	n (%)
≥ 12 years	n (%)	n (%)
p-value	p	p
Race		
White	n (%)	n (%)
African America/Black	n (%)	n (%)
Other	n (%)	n (%)
p-value	p	p
Body mass index		
< 25 kg/m 	n (%)	n (%)
≥ 25 kg/m 	n (%)	n (%)
p-value	p	p
Baseline facial IGA		
Moderate	n (%)	n (%)
Severe	n (%)	n (%)
p-value	p	p
Female who used oral contraceptive*		
Used	n (%)	n (%)
Did not use	n (%)	n (%)
p-value	p	p

Note: The denominator for the percentage is the number of subjects with available data who selected Never/Rarely (N=X for baseline and N=X for week 12)

\*The denominator for the percentage is the number of ‘female’ subjects with available data who selected Never/Rarely (N=X for baseline and N=X for week 12)

